Institutional Review Board Intervention/Interaction Detailed Protocol

Principal Investigator: Dr. J. [name].

Project Title: Effect of Slow Breathing and Yogic-Derived Breathing on Respiration and Cardiovascular Variability in Spinal Cord Injury Patients

Version Date: 5/19/23

Version Name/Number: Version 4

1. Background and Significance

Interest in mind-body medicine, which focuses on interventions such as meditation, yoga & tai chi, bio-feedback, and cognitive behavioral therapy to promote health, has grown significantly in recent years with specific focus on the potential therapeutic effects of slow-breathing (<6 breaths /min or 0.1Hz), and traditional yogic (*pranayama*) breathing practices. Research shows that reduced respiratory rates may impact both blood pressure regulation (1,2) and cardiac autonomic tone (2-4). Moreover, cardiovascular variabilities (Heart Rate Variability (HRV) and Blood Pressure Variability (BPV)) are markedly impacted by breathing pattern and have even been exploited as indices of autonomic circulatory control (5). However, various pathophysiological processes can alter the relationships between breathing rate and depth and cardiovascular variabilities. Of note, Spinal Cord Injury (SCI) results in a variable pathophysiologic profile in which deficits vary with level and degree of injury but can markedly impact both autonomic and respiratory control (6). Therefore, the SCI population may be especially needful of therapeutic slow-breathing interventions to mitigate the impact of altered autonomic control of the heart and blood vessels and to improve the efficiency of respiration. Indeed, individuals with SCI > T6 experience persistent hypotension and bradycardia daily (20). SCI has repeatedly been linked to increased risk for cardiovascular disease (CVD) that may be related to increased BPV and decreased HRV (21, 22). Decreased HRV is associated with cardiac diseases and is prognostic for those with known CVD (23, 24). Moreover, HRV decreases with age, is lower in those with a sedentary lifestyle, and is inversely related to inflammatory markers in both healthy individuals and those with CVD (25). Specific to SCI, HRV is decreased within the first 24 months after injury, suggesting that this decline is mainly to a direct impact of autonomic injury itself rather than lifestyle effects of SCI (26).

It is known that slow breathing can result in a resonance phenomenon in heart rate and blood pressure. (27, 28) This results from low frequency respiratory sinus arrhythmia (RSA), the R-R interval shortening during inspiration and lengthening during expiration. Several studies have examined the effects of traditional slow breathing techniques on heart rate variability (10-13). One systematic review investigating slow breathing in healthy subjects showed that slow breathing rates generally results in greater HRV and greater synchronous BPV. Data from studies comparing three separate meditation techniques found that all practices create prominent low frequency oscillations coupled to the slow respiratory rate (13). In addition, previous studies investigating hemodynamic changes during yogic derived, slow breathing at 0.10 Hz have found decreased blood pressure during the slow breathing period in healthy subjects, subjects with hypertension, and subjects with congestive heart failure (1,2,17-19). Thus, while these findings suggest that slow breathing may induce acute changes in hemodynamics, there is limited insight to

the full effects that reduced respiratory rates may have on control of cardiovascular function, especially in individuals with a spinal cord injury.

c) Study Rationale

The relationship between respiratory patterns and cardiovascular variability in healthy persons has been previously studied. However, the impact of SCI on the interrelationships between the respiratory and cardiovascular systems remains relatively unstudied. The loss of autonomic control in SCI may mean that slow breathing has profound effects on cardiovascular variabilities. Hence, those with SCI may represent a population that could benefit from the potential physiologic effects of numerous yogic-based breathing patterns that can be applied anywhere any time. Hence, it is important to determine if slower breathing patterns can shift the cardiovascular control pattern towards important healthful effects. This physiological study will compare the effects of uncontrolled breathing and traditional yogic slow-breathing practices on cardiovascular variabilities in SCI patients.

2. Specific Aims and Objectives

***Objective 1:** To determine if those with spinal cord injury can successfully perform slow yogic breathing patterns and gain respiratory fitness with daily practice.*

***Hypothesis 1:** Two weeks of at-home practice will result in better performance of respiratory control (maintenance of frequency and volume over time) in those who practice more, however, accurate performance of yogic breathing will be lesser in those with high thoracic injuries (T3-T6).*

***Objective 2:** To assess the respiratory and hemodynamic changes that accompany slow yogic breathing in spinal cord injury patients.*

***Hypothesis 2:** Respiratory rate will decrease, blood pressure will decrease, tidal volume will increase, and minute ventilation will remain unchanged during yogic slow breathing compared to spontaneous breathing.*

***Objective 3:** To discern the changes in the relationship between respiration, heart rate and blood pressure variabilities with yogic breathing.*

***Hypothesis 3:** Slow yogic breathing will shift the relationship between heart rate and blood pressure variabilities toward more synchronized heart rate and systemic blood pressure fluctuations.*

3. General Description of Study Design

This study will be a small (N= 20) prospective cohort study with a one-time unblinded intervention of 4 differing breathing techniques compared to paced breathing. Participants will receive a log for at-home practice and instruction lasting 45 minutes around D1 and D7 with the option to have on coaching session via MGB's Zoom application. On D14 the participant will be asked to sequentially execute the randomized breathing techniques. The lab visit will last approximately 1.5 hours, during which beat-by-beat

cardiovascular variables and breath-by-breath respiratory variables will be recorded while slow breathing. The total in-person time commitment is about 4 hours (**Figure 2**).

[figure not shown]

Figure 2: Study schema with a timeline of participant contact hours and days. There will be two moments of coached practice during a period of two weeks with at-home practice encouraged throughout the period. At the conclusion of the two weeks the breathing practices will be repeated in the laboratory while obtaining respiratory and cardiovascular measurements. *It is possible for the participants to schedule the second visit via MGB's Zoom application.

4. Subject Selection

a) Inclusion/Exclusion Criteria

We will complete studies on 20 individuals — men and women aged 18 to 60 years — with a spinal cord injury. A detailed medical history will be taken, and subjects will be selected based on the following:

Inclusion criteria:

- 1) History of Spinal Cord Injury
- 2) Age: 18-60 years old
- 3) Wheelchair user
- 4) Medically stable & able to follow directions
- 5) Body mass index (18.5 - 35 kg/m²)

Exclusion criteria:

- 1) BP >140/90 mmHg
- 2) Current use of tobacco or cardioactive medications (except medication to support blood pressure)
- 3) Significant arrhythmia
- 4) Coronary artery disease
- 5) Diabetes
- 6) Renal Disease
- 7) Cancer
- 8) Epilepsy or other neurological diseases
- 9) Non-English Speakers

Source of subjects and recruitment methods

All volunteers will be considered regardless of race, ethnicity, or national origin. We plan to study both men and women. We will recruit individuals with a spinal cord injury from the Exercise for Persons with Disabilities (ExPD) program at Spaulding Hospital Cambridge.

Research Assistants will identify eligible individuals during scheduled ExPD workout sessions and from population of past ExPD participants. Where possible eligible individuals will be given a flyer. If the ExPD population is exhausted before reaching our desired number of participants, recruitment can be extended to the general SCI population of Boston via the use of flyers. If eligible and interested participants will be asked to complete a pre-screening phone survey.

5. Subject Enrollment

The principal or co-investigators will obtain volunteer consent in accordance with guidelines established by the Institutional Review Board during the first study visit to the Cardiovascular Laboratory. Participants are encouraged to ask questions and are reminded that participation is strictly voluntary and will not affect their current or future care at Spaulding Rehabilitation Hospital or any of its affiliates. Each subject will be told that he/she will be free to discontinue participation in the experiment at any time and that the investigators reserve the right to discontinue the research protocol at any time. A copy of the signed informed consent form will be given to the subject. All study subjects will participate in the same study protocol, differing only by the randomization of the order of the yogic breathing techniques.

6. Study Procedures

a) Study Components

YOGIC BREATHING INTERVENTION

The subject will receive one-on-one coaching on breathing techniques with the co-investigator two times. The subject may opt to complete the second coaching session via MGB's Zoom application.

The breathing techniques will be varied in:

1. breath frequency (between 0.25 and 0.08 Hz)
2. Inspiratory – Expiratory ratio (I:E) or 'Duty Cycle'
3. with and without ujjayi (yogic throat constriction)
4. with and without inspiratory/expiratory breath holding

AT-HOME PRACTICE

At the end of the first visit the subject will be given a log to record their at-home practice of the breathing techniques they were coached on. Participants will also receive an information pamphlet and audio track with information about the exercises covered during the first coaching session.

b) Study Visits

Pre-Screening

All study subjects from the ExPD program at Spaulding Hospital will be preliminarily screened over the telephone to ensure that they meet preliminary eligibility requirements. Eligible members will be approached after their workouts by the co-investigator to ask permission to call for screening.

Screening

Subjects who meet preliminary eligibility criteria and are interested in participating will be called by the co-investigator to screen inclusion and exclusion criteria and to discuss additional information about the study. Participants will be sent the informed consent letter at least one week before the first visit. Informed consent will be obtained at Spaulding Rehabilitation Hospital, Cambridge.

Visit 1 — History, Baseline, 1st Coaching

During participants first visit the study procedures will be reviewed in detail with study staff, the subject will give a detailed health history and their written informed consent to the principal or co-investigator. The participant will then proceed to complete a baseline pulmonary function test (PFT) lasting about 30 minutes. Leaving about 45 minutes to cover relevant breathing techniques and exercises.

Visit 2 — 2nd Coaching

The second coaching visit can optionally be completed via MGB's Zoom application and will be shorter and more focused on questions, concerns, or struggles of the participant.

Visit 3 — Breathing & Measurement

Two weeks after inclusion, the subjects will return to the cardiovascular laboratory for assessments. All subjects will be instructed to abstain from vigorous exercise for 1 day prior to each study to avoid autonomic and neuroendocrine effects of exercise. In addition, subjects will refrain from caffeine and alcohol for the previous 24 hours and be studied at least 2 hours after a meal. All breathing patterns and techniques will be practiced with the participant before the day of measurement and the participant will also be coached by a pre-recorded audio track during measurement.

Measurements

1) Pulmonary function test

All subjects will perform standard spirometry for spinal cord injury, as describe in (44). The same technician will test all subjects. Subjects will be seated with belts or pant waists loosened and with a nose clip. The maneuver will be demonstrated, and instructions will be given to inhale completely and "blast" the air out. The subject will be encouraged to exhale maximally and sustain the effort at least 6 sec or longer, if possible, depending on the ability and willingness of the subject to continue. The volume-time curve will be recorded on a kymograph, and the flow-volume loop will be electronically displayed for review. An acceptable effort will be a minimum exhalation time of 6 sec with a rapid start and a well-defined early peak in flow that is smooth and continuous. Three acceptable efforts will be obtained.

2) CV Lab Measurement

Throughout the protocol, subjects will lie 30° supine and will be instrumented with a 5-lead EKG, pulse oximeter, finapress with sphygmomanometer, doppler, chest and abdominal belts, a microphone and a face mask with a two-way respiratory valve; for measurements of QRS-complex, SpO₂,

beat-by-beat arterial pressure, brachial blood flow, respiratory excursions, ujjayi sound mixed expired CO₂, ventilation and end-tidal CO₂.

After instrumentation and calibration, the subject will undergo a period acclimation with a resting breathing pattern for ~7 minutes. We will then record the breathing techniques for ~7 minutes each. Other than the acclimation period with resting breathing frequency the order of the other 5 breathing patterns will be randomized. Upon completion subjects will be asked to turn-in their two-week breathing logs. Participants will proceed to perform an exit-PFT and will then be finished with their contribution to the study.

Note: Subjects that completed Lab Visit 3 before 5/19/23 will be invited back to repeat Lab Visit 3 with the addition of dead space ventilation measurements that has been added to this protocol.

7. Risks and Discomforts

The proposed study will utilize non-invasive cardiovascular and respiratory monitoring techniques with minimal risks. The attachment and removal of ECG electrodes and inflation of the blood pressure cuff may cause mild discomfort. Slow breathing may cause hypercapnia and lightheadedness, which quickly resolves when normal breathing resumes.

8. Benefits

a. Benefits to Participating Individuals

There are no direct benefits other than increased knowledge of different traditional breathing practices and their mental and physical effects.

Financial Compensation

Participants in this study will be compensated financially up to \$100USD relative to their time. As completion of all study visits is necessary for analysis participants will be paid \$20 for each study visit they complete. Payments will be made via check and participants SSN will be collected.

Note: Subjects that have already completed the protocol and repeat the LabVisit 3 protocol will be paid \$20 for this additional visit.

b. Benefits to Society

This research may help physicians and scientists to better understand how slow breathing patterns influence the cardiovascular system in persons with SCI, potentially informing future interventional studies in this population.

9. Statistical Analysis

Specific data variables being collected: We will collect data on RR interval, heart rate, blood oxygenation, beat-to-beat blood pressure, brachial blood flow, breathing frequency/depth, ventilation volumes and end-tidal carbon dioxide levels.

b) Data analysis

Data analysis will begin with summary of important variables. Continuous data will be summarized using means and standard deviations, and categorical data will be summarized using frequencies and proportions. Spectral analysis will be used when appropriate. Mean values for these variables will be compared within subjects using t-tests or Wilcoxon Rank Sum tests. Effects of the important covariates including age, BMI, time since injury, and level of injury will be adjusted for via regression analysis. Co-variables will be compared using a t-test or Wilcoxon Rank Sum test in case of continuous variables and they will be compared using chi-squared test and Fisher's Exact test. Significant co-variables will be used in the above regression analysis.

10. Monitoring and Quality Assurance

As these studies represent physiologic investigation and not clinical trials, no formal quality assurance programs will be implemented but will be overseen by the principal and co-investigators.

Safety

All volunteers will be thoroughly screened prior to study. Studies are conducted in a well-supervised hospital facility and subjects are under constant observation by skilled professionals. Appropriately trained laboratory personnel are present during the procedures and continuous cardiovascular monitoring is performed. Procedures are stopped if the volunteer exhibits potentially serious side effects. In the event of adverse reactions or emergency, resuscitation equipment and medical care are immediately available at Spaulding Rehabilitation Hospital. All volunteers are provided a contact number should there be any complications following study.

Adverse Events

Any adverse events will be promptly reported to the Human Research Committee for review according to HRC guidelines. Serious adverse events either expected or unexpected will be reported immediately (within 24 hours of event) by telephone, fax or email followed by a full written report using the PHRC Adverse Event Form within 10 working days/14 calendar days. Mild to moderate unexpected or expected adverse events will be reported in writing using the PHRC Adverse Event Form within 20 working days/30 calendar days.

Confidentiality

Maintaining study participants privacy and keeping personal identifiers confidential is important to the study staff. All research activity including subject screening and data collection will be performed and stored at Spaulding Cambridge. Subject names, contact information, health history, and other information that can be traced back to the subject will be kept separately from data collected for the study. Personal information will be kept in a locked office or on a password-protected computer and away from data. Collected data will have the subject's identification code and some computer software used to collect data will have the date and time marked on the file. Protocol sheets used during data collection will only have the subject's ID. Spaulding Hospital certifies key personnel have completed education on the use of human subjects in compliance with NIH regulations.

11. Privacy and Confidentiality

- ☒ Study procedures will be conducted in a private setting
- ☒ Only data and/or specimens necessary for the conduct of the study will be collected
- ☒ Data collected (paper and/or electronic) will be maintained in a secure location with appropriate protections such as password protection, encryption, physical security measures (locked files/areas)
- ☐ Specimens collected will be maintained in a secure location with appropriate protections (e.g. locked storage spaces, laboratory areas)
- ☒ Data and specimens will only be shared with individuals who are members of the IRB-approved research team or approved for sharing as described in this IRB protocol
- ☒ Data and/or specimens requiring transportation from one location or electronic space to another will be transported only in a secure manner (e.g. encrypted files, password protection, using chain-of-custody procedures, etc.)
- ☒ All electronic communication with participants will comply with Mass General Brigham secure communication policies
- ☒ Identifiers will be coded or removed as soon as feasible and access to files linking identifiers with coded data or specimens will be limited to the minimal necessary members of the research team required to conduct the research
- ☒ All staff are trained on and will follow the Mass General Brigham policies and procedures for maintaining appropriate confidentiality of research data and specimens
- ☒ The PI will ensure that all staff implement and follow any Research Information Service Office (RISO) requirements for this research

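### Hypothesis 1 can be tested as an association between practice and day-14 performance, not isolated as a training effect, and its T3-T6 comparator is undefined

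*Combined protocol and SAP*

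**What the plan says.** Section 3 describes the design: "This study will be a small (N= 20) prospective cohort study".

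Hypothesis 1 (Section 2) has two limbs:
- **Practice.** The hypothesis opens "Two weeks of at-home practice will result in better performance of respiratory control"; read to the end of the clause, the claim is of "better performance of respiratory control (maintenance of frequency and volume over time) in those who practice more".
- **Injury level.** The hypothesis adds that "accurate performance of yogic breathing will be lesser in those with high thoracic injuries (T3-T6"). It does not say with whom this group is compared.

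Measurement of technique performance is confined to day 14. Section 3 says "On D14 the participant will be asked to sequentially execute the randomized breathing techniques", and the Visit 3 text in Section 6 says "We will then record the breathing techniques for ~7 minutes each". At Visit 1 participants "complete a baseline pulmonary function test (PFT) lasting about 30 minutes" and are then coached. Visit 2 is coaching only and may take place by video. An exit PFT follows at Visit 3. Practice between visits is recorded by the participant in a log, and no amount is assigned.

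Eligibility on injury is "History of Spinal Cord Injury" in a wheelchair user, with no limit on level and no target numbers by level.

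Section 9 plans within-subject comparisons of means and regression adjustment for age, BMI, time since injury and level of injury, and only significant covariates enter. It does not list the baseline PFT, gives no model relating practice to performance, and does not say how level is coded.

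**The concern.** The practice limb is worded causally, but the data for it are one performance measurement per person, taken after the practice period, set against an amount of practice that each person chose. People with greater breathing capacity at the start may both practise more and perform better. A positive association could then appear when practice has no effect. The one baseline respiratory measure that the protocol collects is not among the planned covariates.

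On the level limb, eligibility admits injuries both above and below T3-T6, and Section 1 itself says that deficits vary with level. Without a stated comparator or coding, the sign and size of the T3-T6 result depend on a choice made after the data are seen, and on the mix of levels enrolled.

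**Working it through.** **The plan's own figure.** N = 20 comes with no effect size, SD, alpha or power, so it cannot be reproduced. Everything below other than N = 20 is an assumption: two-sided alpha 0.05, effects in SD units, and the correlations shown.

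**1. Practice limb with no true practice effect.** Let *a* be the correlation of baseline capacity with practice and *b* its correlation with day-14 performance. The spurious correlation of practice with performance is *a* × *b*. If FVC correlates *λ* with capacity, the correlation left after adjusting for FVC is

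(*ab* − *abλ*²) / √[(1 − *a*²*λ*²)(1 − *b*²*λ*²)].

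For *a* = *b* = 0.5 and *λ* = 0.7 this is (0.25 − 0.1225) / 0.8775 = 0.145. For 0.6 it is (0.36 − 0.1764) / 0.8236 = 0.223. False-positive rates from 40,000 simulated data sets of 20 (trivariate normal, with FVC added as a noisy copy of capacity):

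| *a* / *b* | Spurious r, unadjusted | Rejects, unadjusted | Rejects, FVC with *λ* = 0.7 | Rejects, FVC with *λ* = 0.5 | Rejects, capacity itself known |
|---|---|---|---|---|---|
| 0.3 / 0.3 | 0.09 | 6-7% | 5-6% | 6% | 5% |
| 0.5 / 0.5 | 0.25 | 19% | 9% | 13% | 5% |
| 0.6 / 0.6 | 0.36 | 35% | 15% | 24% | 5% |

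If baseline capacity is unrelated to practice (*a* = 0), the unadjusted test is already valid at about 5%.

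**2. Precision of the practice limb.** By Fisher's z, the smallest correlation detectable with 80% power at N = 20 is tanh[(1.960 + 0.842) / √17] = tanh(0.680) = 0.59.

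**3. Level limb, if T3-T6 were compared with all others.** Let *d* be the deficit of T3-T6 against injuries below T6, *c* the deficit of injuries above T3 against the same group, and *q* the share of the comparator that lies above T3. The contrast is −*d* + *qc*, which reaches zero at *q* = *d*/*c*.

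| *d*, *c* (SD) | *q* = 0 | 0.25 | 0.5 | 0.75 | Zero at *q* |
|---|---|---|---|---|---|
| 0.5, 1.0 | −0.50 | −0.25 | 0.00 | +0.25 | 0.50 |
| 0.8, 1.5 | −0.80 | −0.43 | −0.05 | +0.32 | 0.53 |
| 0.8, 1.0 | −0.80 | −0.55 | −0.30 | −0.05 | 0.80 |

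Reversal needs *c* > *d* and *q* above *d*/*c*. Power is low in any case: for a true difference of 0.8 SD, a two-sample t test has 27% power with a 4/16 split of the 20 and 40% with 10/10.

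**The case against.** The strongest reply is that the hypothesis predicts better control in those who practise more. That is a comparison between people, and the logs and the day-14 recordings can test it. This stands. A reader might infer that Hypothesis 1 cannot be tested at all. The documents do not support that, and the level limb is cross-sectional and needs no baseline. What remains is the causal wording.

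Nor is Objective 1 left wholly without a before-after measure. The baseline and exit PFTs bear on gains in respiratory fitness, though not on control of frequency and volume. The invited repeat of Visit 3 for earlier participants comes after practice, so it is not a baseline either.

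Section 9 does plan to adjust for injury level, which plausibly determines much of breathing capacity. Where level is retained, part of the bias may already go, and the unadjusted rates above would overstate the problem. But retention depends on significance in a sample of 20.

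On level, a reader might infer that T3-T6 will be compared with everyone else pooled, and that the result will be cancelled or reversed. No section states that comparison, and the documents give no mix of levels. If level were coded in order, Section 9's covariate could come close to the analysis proposed below. The supportable defect is that comparator and coding are unspecified.

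Finally, the study describes itself as small and as a physiologic investigation. That bears on how firmly the results should be worded. It does not justify a causal claim.

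**Conclusion.** The point holds in a limited form. As planned, Hypothesis 1 can show whether people who log more practice perform better on day 14. It cannot show that practice is the reason. With no practice effect, the false-positive rate of an unadjusted test runs from about 6-7% to 35% over assumed correlations of 0.3 to 0.6 with baseline capacity. None of these correlations is in the documents, so this is a range of possible harm and not an estimate.

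A reader might also infer that adding FVC restores the 5% level. That holds only if the confounder itself is measured without error. With a correlation of 0.7 between FVC and capacity, about 9% and 15% remain in the 0.5 and 0.6 cases. Adjustment is worth making because the measurement is already taken, but the conclusion must still be worded as an association.

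The level point is secondary. The T3-T6 comparator and the coding of level need to be stated. A contrast with all other levels could shrink or reverse, but only if higher injuries perform worse than T3-T6 and form a large enough share of the comparator.

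**What to change.** 1. **Practice analysis.** In Section 9, specify a regression of day-14 performance error on logged practice, with baseline FVC from the Visit 1 spirometry as a covariate whatever its significance. Define the error measure in advance for both frequency and volume.
2. **Wording.** Report the result as an exploratory association between practice and performance, not as an effect of practice.
3. **Level analysis.** Code level in three ordered categories (above T3, T3-T6, below T6), kept irrespective of significance, and use these in place of any contrast of T3-T6 with all others. Do not adjust this analysis for FVC, because FVC lies on the path from injury level to performance.

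The cost is analysis wording and one degree of freedom for FVC at N = 20. No new data are needed.

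A recording of technique performance before practice would be a stronger baseline, but the fix does not depend on it. Chest and abdominal belts alone, with no volume calibration described, would not give volume on the scale of the Visit 3 face mask, and participants already past Visit 1 would have no such recording.

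### Hypothesis 2 predicts unchanged minute ventilation, but Section 9 plans only difference tests and regression, with no margin or confidence interval, so nothing in the plan can support that prediction

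*Combined protocol and SAP*

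**What the plan says.** Hypothesis 2 (Section 2) has four parts. Three are directional: respiratory rate and blood pressure fall, and tidal volume rises. The fourth predicts no change: "minute ventilation will remain unchanged during yogic slow breathing compared to spontaneous breathing".

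The analysis is in Section 9, b) Data analysis. The descriptive part reads "Continuous data will be summarized using means and standard deviations". The comparison is "Mean values for these variables will be compared within subjects using t-tests or Wilcoxon Rank Sum tests". The regression step is "Effects of the important covariates including age, BMI, time since injury, and level of injury will be adjusted for via regression analysis". Spectral analysis is added where appropriate. Minute ventilation is not named there, but the collected variables include "breathing frequency/depth, ventilation volumes and end-tidal carbon dioxide levels".

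Section 3 gives the size and design: "This study will be a small (N= 20) prospective cohort study". Section 4 repeats the 20. No alpha, power, SD, effect size or equivalence margin appears anywhere, and there is no rule for concluding that ventilation is unchanged.

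The reference condition is not consistent. Hypothesis 2 compares with spontaneous breathing, while Section 3 describes four techniques compared with paced breathing. In Section 6 b), Visit 3 begins with a resting-breathing period of about 7 minutes, followed by five patterns in random order.

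**The concern.** A prediction of no change is an equivalence claim. A difference test can contradict it but cannot support it, because a non-significant result is also what a real change gives when measurement is noisy or the sample small. Section 9 handles this part of Hypothesis 2 exactly as it handles the three directional parts. For those, noise makes the hypothesis harder to support. For minute ventilation, noise makes a result that looks like confirmation more likely.

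At stake is the conclusion on one stated part of one of three hypotheses. A true fall in minute ventilation of 10% or 15% could go undetected, and the plan provides no interval to show readers which changes the data leave open.

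**Working it through.** **Inputs from the documents.** 20 participants, each their own control (Sections 3 and 4), and a within-subject t-test (Section 9). The plan gives no inputs behind N = 20, so that figure cannot be reproduced.

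**Assumptions.** Two-sided alpha of 0.05 for the difference test, and two one-sided tests at 0.05 each (equivalently a 90% confidence interval) for equivalence. The SD of the paired difference is taken as 10% to 30% of reference ventilation. Percentages stand in approximately for log-scale changes.

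**Step 1: precision.** The half-width of the interval is t × SD/√20 with 19 degrees of freedom.
- 95%: 2.093/4.472 = 0.47 SD.
- 90%: 1.729/4.472 = 0.39 SD.

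At SD 20% the 95% interval is therefore about ±9.4 percentage points. At SD 30% it is about ±14.0.

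**Step 2: chance that a real fall is non-significant.** With standardised change d = true fall/SD, the test statistic follows a non-central t distribution with 19 degrees of freedom and non-centrality d√20. The chance is the probability that it lies between −2.093 and 2.093. Example: a 10% fall at SD 20% gives d = 0.5, non-centrality 0.5 × 4.472 = 2.236, and probability 0.44.

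| Assumed SD | True 10% fall: d | Non-significant | True 15% fall: d | Non-significant |
|---|---|---|---|---|
| 10% | 1.00 | 1% | 1.50 | about 0% |
| 15% | 0.67 | 19% | 1.00 | 1% |
| 20% | 0.50 | 44% | 0.75 | 11% |
| 25% | 0.40 | 60% | 0.60 | 28% |
| 30% | 0.33 | 71% | 0.50 | 44% |

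The difference test reaches 80% power only at d = 0.66.

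**Step 3: what 20 pairs can establish by equivalence testing.** Power was computed for a true change of zero, integrating over the sampling distribution of the SD. It is 39% for a margin of 0.5 SD, 65% for 0.6 SD and 83% for 0.7 SD, and reaches 80% at about 0.68 SD. In percentage terms, 0.68 SD is about 10%, 14%, 17% and 20% at SD 15%, 20%, 25% and 30%.

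Taking ±15% purely as an example, the margin is 15/25 = 0.6 SD at SD 25% (power 65%) and 15/30 = 0.5 SD at SD 30% (power 39%).

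**The case against.** The best reply is that Section 9 nowhere says a non-significant result will count as proof. That is correct. A reader might infer such a rule, but the documents state none. What stands is narrower: the plan contains no other inferential route to supporting the prediction. Means and SDs are planned too, but they do not test it, and the covariate regression does not test equivalence.

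The size also rests on an assumed SD. At 10% the problem nearly vanishes for both falls considered, and at 15% it is small for a 15% fall. That too is correct, and it is why the full range is shown.

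Two stronger readings are tempting and not supported:

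- *That real hypoventilation would be reported as no change.* Section 7 does mention possible hypercapnia. But a lower minute ventilation with larger breaths is not in itself hypoventilation. With purely assumed values of 0.15 L dead space and 15 breaths/min at 0.5 L, total ventilation is 7.5 L/min and alveolar ventilation 15 × 0.35 = 5.25 L/min. At 6 breaths/min the same alveolar ventilation needs 5.25 + 6 × 0.15 = 6.15 L/min in total, an 18% fall. The study also records end-tidal CO₂ and oxygen saturation, and has added dead space measurements.
- *That the hypothesis requires tidal volume to rise about threefold.* The ratio 0.25/0.08 = 3.1 compares the two ends of the range over which the techniques vary (Section 6 a)). Hypothesis 2 compares with spontaneous breathing, whose rate is not given.

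Finally, this is one of four parts of one hypothesis in a study that Section 10 describes as physiologic investigation, with no primary endpoint named. That limits the severity but does not remove the mismatch.

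**Conclusion.** The concern holds in a limited form. The prediction of no change in minute ventilation has no analysis that could support it, and a non-significant paired test from 20 people would not do so. Under the stated assumptions, the chance of missing a true 10% fall runs from about 1% (SD 10%) to 71% (SD 30%), and of missing a true 15% fall from about 0% to 44%. The SD is unknown from the documents, so no single figure in these ranges can be called the study's own. N = 20 is not shown to be too small: it suits an equivalence margin of roughly 0.7 SD or wider. The point should be fixed before analysis, but it does not threaten the study as a whole.

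**What to change.** In Section 9, add that minute ventilation will be analysed as the paired log-scale change for each yogic technique against the spontaneous (resting) breathing period named in Hypothesis 2, reported with a 90% confidence interval. Allow a conclusion of no change for a technique only if its interval lies wholly inside a margin justified and fixed before analysis (two one-sided tests). If no margin can be justified, report the estimate and interval and make no such claim. The sponsor must choose the margin; the ±15% used above is only an example.

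Reconcile Hypothesis 2 with Section 3, which names paced breathing as the comparator, so that the reference condition is fixed.

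The cost is a few sentences and agreement on a margin, with no added participants, visits or measurements. The downside is real: the study may be unable to claim no change. With 20 pairs, 80% power needs a margin of about 0.68 SD, and an example margin of ±15% would succeed in only about 65% of studies at SD 25% and 39% at SD 30%, even if the true change were zero.
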